8.0 Data Analyses

8.1. General Considerations. Primary study analyses will be conducted on an intent-to-treat basis, with participants analyzed in the group to which they were assigned. Additional exploratory analyses focusing on more restrictive analytic cohorts (e.g., per protocol analysis) will be considered, to provide additional information about the impact of magnitude of exposure to the intervention. The main conclusions drawn from this trial will be based on the pre-specified primary and secondary hypotheses outlined below and will be tested with two-sided p-values at the standard 0.05 level unless noted otherwise. Statistical analyses will be performed using SAS for Windows (Version 9.2: SAS Institute, Cary, NC) and R (<http://www.R-project.org/>).

8.2. Primary Analysis (Specific Aim 1). The main study outcome, WOMAC, is a continuous measure collected at baseline, 3, 6, 9 and 15 months (STEP-KOA group only). For the primary hypothesis we will examine STEP-KOA effects at the 9-month assessment. We will use a linear mixed model (LMM) that accounts for the correlation between a participant's repeated outcome measurements over time. We will apply an unstructured covariance matrix to take into account the within-patient correlation between repeated measures. The fixed-effect portion of the model will have the form: $Y_{it} = \beta_0 + \beta_1 3\text{month} + \beta_2 6\text{month} + \beta_3 9\text{month} + \beta_4 \text{STEP-KOA} * 3\text{month} + \beta_5 \text{STEP-KOA} * 6\text{month} + \beta_6 \text{STEP-KOA} * 9\text{month}$, where Y_{it} is the WOMAC score for subject i at $t=0, 3, 6, \text{ and } 9\text{months}$. We will estimate the parameters in the model and set up contrasts for tests of hypotheses using the SAS procedure MIXED (Cary, NC). Specifically, for Hypothesis 1, we will test for a difference in mean WOMAC scores between the STEP-KOA and AE groups at 9-months by testing that $\beta_6=0$.

Time is coded in the model to fit a constrained longitudinal data model (cLDA), in which baseline WOMAC score is modeled as a dependent variable in conjunction with the constraint of a common baseline mean across treatment arms⁸³. For improvement in precision, the model will be adjusted for stratification variables⁸⁴.

8.3. Secondary Analyses. Since the secondary outcomes, 30 second chair stand and 40 meter fast-paced walk, are continuous, longitudinally collected measures, we will use similar modeling procedures as those described above for WOMAC scores to assess between-group differences at 9-month follow-up. We will also examine Poisson or negative-binomial mixed models as a sensitivity analysis as these outcomes (particularly chair stands) can be skewed and assumption of a normal distribution may not be reasonable.

For Specific Aim 2, to examine the maintenance effects of STEP-KOA at the 15-month follow-up, we will add the 15-month outcomes and the 15-month time-point to the fixed effect portion of the model. As we will only be estimating the maintenance effects for participants randomized to the STEP-KOA arm, we will drop the treatment by time variables from the fixed effects. We will set up contrasts of model parameters to estimate the difference and associated 95% confidence intervals in outcomes between the 9-month and 15-month time points. Models will also be fit to estimate these differences for subgroups defined by the combination of steps received during the STEP-KOA program by adding variables to the fixed effects indicative of the steps received as well as their interactions with time.

For Specific Aim 3, we are interested in understanding the flow of responders and non-responders through the STEP-KOA intervention. Our goal is to determine whether there are patient-level factors, already known or easily determined in routine clinic visits, which could be used by providers (individually or in combination), to guide referral of patients to a Step that is most likely to meet their needs. We will first calculate proportions of responders and non-responders at each time point and describe responder patterns longitudinally. We will also calculate proportions of individuals who meet response criteria in the two-different way described in Section C.5.1. We will then examine characteristics associated with responder status at each time point, using multivariable logistic regression models. In these models, we will first focus on the four *a priori* patient characteristics: age, baseline pain and function, and baseline self-rated health, to avoid spurious statistical findings⁸⁵. Based on clinical experience, we believe these variables have potential to predict response, and they can be assessed easily and quickly, making them practical screening tools.

8.4. Missing Data. Because the main predictors of interest, intervention arm and patient characteristics, are collected at baseline, we do not anticipate much missing data in these variables. There may be missing values in the follow-up outcome measures due to dropout, death, a missed interim assessment, or item non-response. Our main analysis technique for the primary outcomes, general linear mixed models via maximum likelihood estimation, implicitly accommodates missingness when missingness is due either to treatment, to prior outcome, or to other baseline covariates included in the model, defined as missing at random^{86,87}. If the missing values are related to other measured patient factors, then multiple imputation (MI) provides a framework for incorporating information from these variables, while still preserving a parsimonious main treatment effect model^{88,89}. Depending on the type and scope of missing data, MI will be conducted via the SAS procedure PROC MI or the SAS macro IVEware (<http://www.isr.umich.edu/src/smp/ive/>).

8.5. Sample Size. The sample size estimate of n=345 patients is based on a 2:1 randomization and the comparison of the primary outcome between the STEP-KOA and AE control arms at 9 and 15 months. Since AIM 3 is to describe the responder patterns for the Step progression in STEP-KOA we are using a 2:1 randomization to facilitate our ability to evaluate these patterns⁹⁰. For sample size calculations we used methods appropriate for ANCOVA type analyses⁹¹, which are equivalent in terms of efficiency to our linear model in randomized trials⁸³. This method is based on performing a two-sample t-test sample size calculation for the between group difference, multiplied by a factor $1 - (\rho)^2$, where ρ represents the Pearson correlation between baseline and follow-up time point outcome measures. This sample size is then inflated to compensate for potential missing observations due to attrition. We estimate a 20% attrition rate at the 9-month time point, which is conservative based on our other clinical trials among Veterans with OA, all of which have had attrition rates <20%, including one that required two or more in-person visits from participants^{16,26,44}. Also, based on our previous data, we assume a correlation of 0.4 between baseline and follow-up WOMAC scores, and an SD of 17.5. With 80% power, $\alpha=0.05$, $SD=17.5$, $\rho=.4$, and approximately 20% attrition rate by 15-months, 230 and 115 participants are needed in the STEP-KOA and AE groups, respectively, for an effect

size of 0.33. This corresponds to a 5.8 point difference in mean total WOMAC scores at 9-months between STEP-KOA and AE, which is a clinically relevant improvement ⁴³. We will also be powered to detect medium effect size differences in secondary study outcomes. For Aim 3, based on an assumption of 1/3 responders after Step 1, we would have about 154 participants that progress to Step 2; additional participants who initially meet response criteria at three months may regress at six-months and enter Step 2 at that time point. We also expect that about 1/3 of the total STEP-KOA group (about n=76) will progress to Step 3.

9.0 Economic Evaluation. The overall goal of Specific Aim #4 is to provide the VA with information about the value of the STEP-KOA program, from a cost effectiveness perspective. In addition to informing the VA regarding the overall average cost of STEP-KOA per patient, this evaluation will provide information on how much improvement in outcomes can be achieved for that cost. This information is important for evaluating the potential for downstream implementation of STEP-KOA under various assumptions about scale and scope. We will not evaluate differences in costs or cost effectiveness according to the number of Steps each participant received; rather this will be a simple approach that is consistent with using the VHA perspective and comparing total aggregated costs across the two study arms (STEP-KOA vs. AE) at the 9-month follow-up point. The analysis will begin with descriptive statistics of the cost and effectiveness (utility) data. We will examine each measure of effectiveness, WOMAC and mean QALY (and the scores on the different EQ-5D-5L attributes, such as pain/discomfort), using the general analytic procedures and time points described above for primary and secondary outcomes. We will calculate the incremental cost effectiveness ratio (ICER) of STEP-KOA compared to the AE control group, separately for WOMAC and QALYs. The ICER will be calculated as the difference in the average total cost per participant STEP-KOA and AE, divided by the difference in the average effectiveness per participant between STEP-KOA and AE. Bootstrapping of estimates, multiple imputation for missing EuroQoL values, and sensitivity analyses will all be conducted to ensure robustness of our results.

10.0 Data Management and Quality Control. Study tracking and randomization functions will be completed with a database previously created in our Center with Microsoft .NET. Screening and outcome measures, as well as content and results of Step 2 physical activity counseling calls, will be recorded using DatStat Illume™, a web-based survey tool. The VET-KOA website is hosted by Visual Health Information. The study team will give each participant a unique code. They will use this code to initially log in. The link between participants' unique codes to access the website and other participant information will be kept on a computer server at the Durham VA, accessible only to IRB-approved study team members. So when the website vendor sends information to the VA team at the end of the study (e.g. on participants' website usage), the VA study team will be able to link this to each participant. When this information on website usage is conveyed to VA at the end of the study, it will be done so using a VA approved method (e.g., encrypted CD). The information that the vendor will supply to VA by the end of the study includes: self-reported pain, physical function, and physical activity, as well as whether they reported an increase in pain after completing their exercises.

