7.0 Measures

Study assessments will be conducted in person at baseline and 9-months (primary outcome point); interim assessments (3-months, 6-months) and longer-term follow-up (15-months) will be conducted via telephone. Assessments will be conducted by a research assistant blinded to group assignment. Participants will be paid \$40 for in-person and \$20 for telephone-based assessments. This measurement battery is shorter in length than those from our recent clinical trials among veterans with knee OA^{26,44}, and the time burden has been

acceptable to participants, with little missing data. Prior to each assessment point (either on the phone at the time of scheduling, on the phone just before assessments begin, or in-person at the time of assessment), a study team member will ask participants whether they have had any new health problems since their last assessment point. If there are new health problems, the study team will ask the nature of these problems. If these problems are related to exclusion criteria, the study team member will either: 1) Let the participant know they need to be withdrawn from the study OR 2) If it is unclear whether withdrawal is appropriate, let the participant know they will contact a clinical co-investigator and follow-up to let them know if they are eligible to continue in the study; assessments will not proceed until this is resolved. At in-person follow-up visits, research assistants will measure the participants Resting Blood Pressure; if diastolic blood pressure >110mm/Hg or systolic >200mm/Hg will be advised to be seen at the Emergency Department or Urgent Care immediately. Assessments will not proceed until these issues are resolved.

7.1 Primary Outcome: WOMAC. The primary outcome measure is the WOMAC, a measure of lower extremity pain (5 items), stiffness (2 items), and function (17 items), with items rated on a Likert scale of 0 (no symptoms) to 4 (extreme symptoms). The reliability and validity of the WOMAC total score and subscales have been confirmed⁷⁴. The WOMAC has been widely used in trials behavioral interventions for knee OA, confirming its sensitivity to change. The WOMAC has also been validated for use via telephone⁷⁵. To supplement the WOMAC, we will add additional measures that are part of the widely used Knee Osteoarthritis Outcome Survey (KOOS).

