7.2 Secondary Outcome: Objective Physical Function. We will assess physical function using measures recommended by OARSI for clinical trials of knee OA⁷⁶. These tests have been previously validated, with strong measurement properties and sensitivity to change in clinical trials among patients with OA. These tests will include a 30 second stair stand test, a 40m fast-paced walk, a timed get up and go test, stair climbing test, and a 6-minute walk test, following previously established procedures for each. The 30 second stair stand asks participants to rise and sit back down in a chair as many times as they can during that time period, without using hands or arms for support⁷⁷. The 40m fast-paced walk is a timed test of walking twice back and forth (as fast as participants are able) over a 10m distance⁷⁸. The timed get up-and-go test requires the participants to stand from a standard arm chair, walk 3 meters and then return to sitting in the same chair (as quickly and safely as possible). The stair climbing test measures the time it takes to ascend and descend a flight of 12 steps (each step 18 cm high and 28 cm deep). Participants will be asked to complete the test as quickly as they felt safe and comfortable. The use of one handrail will be allowed if necessary, but patients will be encouraged to minimize their use of the handrail. The 6-minute walk test will require participants to walk as far as they can during a 6-minute periods. Walking aids are permitted as needed. Participants will be asked to walk the amount of time they are able to walk. Following these tests, we will ask participants to indicate the maximum pain they experienced, on a scale of 0-10, during the test.

7.3 Self-Efficacy for Exercise Scale. The Self-Efficacy for Exercise scale assesses individuals' confidence in engaging in exercise in nine different situations that could present barriers (including having pain when exercising)⁷⁵. For each situation, individuals are asked to rate their confidence in being able to exercise three times a week for 20 minutes each time, on a scale of 0 (not confident) to 10 (very confident). Validity of this measure was confirmed by expected associations with actual exercise, as well as physical and mental health.

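### The Poisson or negative-binomial sensitivity analysis also covers the 40 m walk, which is a time; a Poisson model would make its p-value depend on the time unit analysed

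*Combined protocol and SAP*

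**What the plan says.** Section 8.3 (Secondary Analyses) treats the two outcomes together: "Since the secondary outcomes, 30 second chair stand and 40 meter fast-paced walk, are continuous, longitudinally collected measures". Both get the constrained longitudinal linear model of section 8.2. The sensitivity analysis follows: "We will also examine Poisson or negative-binomial mixed models as a sensitivity analysis as these outcomes (particularly chair stands) can be skewed". The reference is to both outcomes. The parenthesis stresses chair stands but does not leave the walk out.

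Section 7.2 gives the two scales. In the chair stand, participants "rise and sit back down in a chair as many times as they can during that time period", which is a count. For the other, "The 40m fast-paced walk is a timed test of walking twice back and forth", which is an elapsed time.

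Section 7.0 places the performance tests at two visits: "Study assessments will be conducted in person at baseline and 9-months (primary outcome point"). Section 8.1 says hypotheses "will be tested with two-sided p-values at the standard 0.05 level unless noted otherwise".

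The documents give no time unit or rounding rule for the walk, no estimated scale parameter or robust standard error for the count models, no other skewed-data model for the walk, and no rule for choosing between Poisson and negative-binomial.

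**The concern.** A Poisson likelihood ties the variance to the mean. For a count that is a meaningful assumption. For a time it is not: changing the unit by a factor c multiplies the mean by c and the true variance by c squared, while the model lets the variance rise only by c. A random intercept absorbs differences between patients, but the within-patient variance on the log scale stays fixed at about 1/mean, whatever the data show. The arm comparison at 9 months rests on that within-patient part.

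At stake is whether the robustness check on one of the two named secondary outcomes says anything about robustness. Under Poisson it can be too cautious or far too liberal on the same data, depending on a unit that the plan leaves open.

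**Working it through.** **1. Arm sizes, from the plan's own sample size (section 8.5).** Inputs: "we assume a correlation of 0.4 between baseline and follow-up WOMAC scores, and an SD of 17.5"; effect size 0.33, of which the plan says "This corresponds to a 5.8 point difference in mean total WOMAC scores at 9-months"; 80% power, two-sided 0.05, 2:1 allocation, 20% attrition.

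- Control arm, two-sample formula: (1.96 + 0.84)² × 17.5² / 5.8² × (1 + 1/2) = 107.2.
- Times 1 − 0.4² = 0.84: 90.0. Divided by 0.80: 112.5, so 113 and 226, total 339 (342 using 0.33 directly).
- The plan states 345, so it is reproduced within 2%. Completers are 0.8 × 230 = 184 and 0.8 × 115 = 92, with power 80.8%.

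The sample size is not in dispute. It only sets the arm sizes below.

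**2. Why the unit matters under Poisson.** Take the arm-by-time comparison with patient intercepts at two visits. In each arm of size n, the log of (sum at 9 months / sum at baseline) has

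- true variance of about 2 × (SD/mean)² × (1 − r) / n, which does not depend on the unit;
- Poisson model variance of about 2 / (n × c × mean), with the mean in seconds and c = 1 for seconds, 10 for tenths, 100 for hundredths.

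The z statistic is therefore too wide or too narrow by k = √[c × SD² × (1 − r) / mean], and the type I error is 2 × [1 − Φ(1.96/k)]. The estimate does not move; z grows as √c. From seconds to tenths that is a factor of √10 = 3.16.

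**3. Numbers.** The mean (30 s), SD (5, 8, 12 s) and test-retest r (0.6, 0.9) are assumptions. Type I error for Poisson at nominal 5%:

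| SD, r | seconds | tenths | hundredths |
|---|---|---|---|
| 5 s, 0.9 | k 0.29: 0% | k 0.91: 3% | k 2.89: 50% |
| 5 s, 0.6 | k 0.58: 0.1% | k 1.83: 28% | k 5.77: 73% |
| 8 s, 0.9 | k 0.46: 0% | k 1.46: 18% | k 4.62: 67% |
| 8 s, 0.6 | k 0.92: 3% | k 2.92: 50% | k 9.24: 83% |
| 12 s, 0.9 | k 0.69: 0.5% | k 2.19: 37% | k 6.93: 78% |
| 12 s, 0.6 | k 1.39: 16% | k 4.38: 65% | k 13.86: 89% |

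Simulating the same test with log-normal times, 184 against 92 patients and 4,000 trials per setting, agrees within about 2 percentage points. In minutes the rate is 0% throughout.

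**4. Full mixed models, Poisson and negative-binomial.** Maximum-likelihood random-intercept models with a common baseline mean, two visits, mean 30 s, between-patient CV 0.25 and within-patient CV 0.10 or 0.20 (assumed). The p-values are from one simulated data set per CV, analysed in four units:

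| Model, within CV | min | s | 0.1 s | 0.01 s |
|---|---|---|---|---|
| Poisson, 0.10 | 0.657 | 0.234 | 0.192 | 0.001 |
| Poisson, 0.20 | 0.988 | 0.635 | 0.060 | <0.001 |
| Neg. binomial, 0.10 | 0.655 | 0.233 | 0.328 | 0.325 |
| Neg. binomial, 0.20 | 0.988 | 0.713 | 0.794 | 0.806 |

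Rejection with no true effect (186 and 170 simulated trials, so a standard error of roughly 1.7 points near 5%):

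| Model | min | s | 0.1 s | 0.01 s |
|---|---|---|---|---|
| Poisson | 0% | 0.5–8% | 29–52% | 76–85% |
| Neg. binomial | 0% | 0.5–3.5% | about 5% | about 5–6% |

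The negative-binomial can add variance to Poisson but not remove it. It is therefore conservative where the squared CV is below 1/mean, and behaves like a gamma model at fine units.

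**5. After the change.** On log time, a change of unit shifts only the intercept, so the p-value stays the same: 0.341 and 0.838 in the two data sets above, by ANCOVA on log time. ANCOVA on seconds, a stand-in for the planned linear model, rejected in 4.8% and 4.7% of the null trials.

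**The case against.** The emphasis on chair stands suggests that the authors chose count models mainly for the count. That is plausible, but an analyst following section 8.3 would fit them to the walk as well.

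The percentages depend on assumed inputs: in seconds alone they run from 0 to about 17% across the assumed SDs and correlations. This stands. Only the dependence on the unit follows from the algebra without assumptions.

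An estimated Poisson scale parameter would remove the unit dependence. In the two data sets, a Poisson model with estimated scale (without a random effect) gave one p-value in all units, 0.030 and 0.946. The plan does not provide for one.

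Four stronger readings are tempting and not supported:

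- A reader might infer that stopwatch precision drives the result. It does not. Times recorded to 0.01 s but analysed in seconds behave like whole seconds (3.6% against 3.7% at SD 8 s, r = 0.6). The large error rates need times multiplied by 10 or 100, for instance to obtain integers, and no section plans that.
- A reader might infer that both models inflate type I error. Only Poisson does.
- A reader might infer that these models cannot deal with a skewed time. A log-link model with a normal random intercept does produce right-skewed data, and at fine units the negative-binomial is close to gamma. The fault is in the Poisson variance, not in the handling of skewness.
- A reader might infer that the check could overturn the trial's main result. Section 8.3 makes it a sensitivity analysis after the linear mixed model, and section 8.1 rests the main conclusions on the pre-specified hypotheses.

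**Conclusion.** The point holds, at low severity. As written, section 8.3 applies count models to a timed outcome, and under Poisson the standard error and p-value for the 40 m walk depend on the unit analysed. With a mean of 30 s, SD 5 to 12 s and test-retest correlation 0.6 to 0.9, all assumed, the Poisson type I error is about 0 to 17% in seconds, 3 to 65% in tenths and 50 to 89% in hundredths. The negative-binomial alternative is too cautious in minutes or seconds and about right at finer units; that rests on the smaller simulation with assumed CVs. Because the plan has no rule for choosing between the two, the Poisson result remains available. Only a sensitivity analysis of one secondary outcome is affected. The primary WOMAC analysis, the linear model for the walk and N = 345 are not.

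**What to change.** In section 8.3, limit the Poisson and negative-binomial mixed models to the chair-stand count. For the 40 m walk, name one sensitivity analysis for skewness:

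- the same constrained longitudinal model on log time, reported as a ratio of geometric means; or
- a gamma mixed model with log link, reported as a ratio of arithmetic means.

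The two estimate different ratios, so the report should say which is used. Either gives the same treatment p-value in any time unit.

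This is one sentence in the plan. It needs no new data, no change in sample size and no change to the main analyses.
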